7. STATISTICAL ANALYSES

7.1. Subject Disposition

For all subjects screened in the study, the following will be summarized:

- Number of subjects screened in the study
- Frequency (number and percentage) of subjects who discontinued the study before randomization, overall and by reason for discontinuation. Percentages will be calculated based on the number of subjects screened in the study

In addition, the frequency of subjects in each of the analysis sets described in [Section 5](#) will be summarized by treatment arm. Percentages will be calculated only for analysis sets that are a subset of the FAS or a subset of the safety analysis set.

The following summaries will be presented by treatment arm based on the FAS:

- Frequency of subjects in each randomization strata and combination of randomization strata (per IRT)
- Frequency of subjects in each randomization strata and combination of randomization strata (as derived from data in the eCRF)
 - De novo AML from the Underlying AML Diagnosis eCRF, the “Specify Nature of AML per Investigator” field with the option “de novo” selected
 - Secondary AML from the Underlying AML Diagnosis eCRF, the “Specify Nature of AML per Investigator” field with any of these options selected, “treatment-related AML”, “history of MDS”, “history of MPD”, or “other”
 - Geographic region will be based on the country code from the Demographics eCRF
- Frequency of subjects randomized in each geographic region, country, and site
- Frequency of subjects randomized and not treated, overall and by reason for discontinuation
- Frequency of subjects with study drug ongoing (separately for each study drug)
- Frequency of subjects who discontinue study drug, overall and by the reason for discontinuation of study drug (separately for each study drug)
- Frequency of subjects ongoing in the study
- Frequency of subjects who discontinue the study, overall and by the reason for study discontinuation

The frequency of subjects with disposition reason, in each epoch, due to reasons associated with COVID-19 will further be summarized under the main reason for discontinuation.

In addition, the following cross-tabulations will be performed:

- Cross-tabulation of randomization strata by IRT vs randomization strata as derived from data in the eCRF

- Cross-tabulation of subjects randomized (AG-120+azacitidine, placebo+azacitidine, none) vs subjects who have received at least 1 dose of study drug (AG-120+azacitidine, placebo+azacitidine, none)
- Cross-tabulation of subjects who have discontinued/are ongoing treatment with AG-120 or matched placebo vs subjects who have discontinued/are ongoing treatment with azacitidine

Disposition for all screened subjects and randomization data will be provided in by-subject listings.

7.2. Protocol Deviations

All major protocol deviations that impact the safety of the subjects, the conduct of the study, or the evaluation of the study results will be reported by treatment arm based on the FAS. These will include:

- Subjects randomized despite not satisfying the eligibility criteria
- Subjects who develop withdrawal criteria while on the study but are not withdrawn
- Subjects who receive a study drug different from that assigned at randomization
- Subjects who are randomized under the wrong stratification factor(s)
- Subjects who receive an excluded concomitant medication

In addition, for each category of major protocol deviations, those related to COVID-19 will be summarized.

Major protocol deviations will be provided in a by-subject listing.

7.3. Demographic and Other Baseline Characteristics

The following summaries will be presented by treatment arm and overall based on the FAS, unless otherwise specified.

7.3.1. Demographics and Physical Measurements

Demographic characteristics and physical measurements at baseline will be summarized as follows:

- Demographic characteristics
 - Sex: male, female
 - Race: American Indian or Alaska Native, Asian, Black or African American, Native Hawaiian or other Pacific Islander, White, other, unknown
 - Ethnic origin: Hispanic or Latino, not Hispanic or Latino, not reported
 - Age (years): summary statistics
 - Age categories:

- <65 years, ≥65 years
- <75 years, ≥75 years
- Physical measurements
 - Height (cm)
 - Weight (kg)
 - BMI (kg/m²)
 - BSA (m²)

Demographic data for all screened subjects will be provided in a by-subject listing.

7.3.2. Disease Characteristics

The following baseline characteristics of the underlying disease will be summarized based on the data entered in the eCRF:

- Disease type
 - Nature of AML per Investigator [de novo; secondary (treatment-related AML; history of MDS; history of MPD; other)]
 - WHO classification of AML (AML with genetic abnormalities; AML with myelodysplasia-related changes; therapy-related myeloid neoplasms; AML not otherwise specified)
- ECOG PS at baseline (0; 1; 2; 3; 4)
- IDH1 mutation type at baseline based on central testing (R132C; R132G; R132H; R132L; R132S; wild type). Results from bone marrow will be used as the primary source. If results from bone marrow are not available, the results from peripheral blood will be used instead.
- IDH1 mutation status at baseline based on local testing (positive; negative)
- Cytogenetic results (normal karyotype; abnormal karyotype) and cytogenetic risk status according to the Investigator based on NCI NCCN guidelines (favorable; intermediate; poor; other)
- Baseline bone marrow aspirate blasts (%)
- Baseline bone marrow biopsy blasts (%)
- Baseline peripheral blood blasts (%)
- Baseline values of the following laboratory parameters. These parameters will be summarized as continuous variables as well as categorical variables using the specified category:
 - WBC (<15×10⁹/L; 15 to <30×10⁹/L; ≥30×10⁹/L)
 - ANC (<0.5×10⁹/L; 0.5 to <1×10⁹/L; ≥1.0×10⁹/L)
 - Hemoglobin (<80 g/L; ≥80 g/L)

- Platelet count ($<50 \times 10^9/L$; 50 to $<100 \times 10^9/L$; $\geq 100 \times 10^9/L$)
- Lactate dehydrogenase (LDH)
- Creatinine clearance (<15 mL/min; 15 to <40 mL/min; 40 to <60 mL/min; 60 to <90 mL/min; ≥ 90 mL/min)
- Extramedullary disease at baseline (yes; no; unknown; not assessed)

Data on disease characteristics will be provided in by-subject listings.

7.3.3. Medical History

Medical history will be summarized in frequency tabulations according to the latest version of the Medical Dictionary for Regulatory Activities (MedDRA) by System Organ Class (SOC) and Preferred Term (PT).

Medical history will be provided in by-subject listings.

7.3.4. Prior Therapies

The following summaries will be presented by treatment arm and overall based on the safety analysis set.

Prior medications are defined as medications (from the Prior and Concomitant Medications eCRF) that are started before the start of study treatment.

All non-study medications will be coded according to the Anatomical Therapeutic Chemical (ATC) code and PT using the latest version of the WHO Drug Dictionary. All prior medications will be summarized in frequency tabulations according to the WHO ATC third level and PT.

Prior procedures are defined as procedures (from the Prior and Concomitant Procedures eCRF) that are started before the start of study treatment.

The prior procedures will be coded according to the latest version of the MedDRA by SOC and PT and will be summarized in frequency tabulations by SOC and PT.

7.4. Exposure to Study Drug and Compliance

The following summaries will be presented by treatment arm based on the safety analysis set. The derivations are provided for the following study drugs:

- AG-120 or matched placebo administered orally at a dose of 500 mg QD
- Azacitidine administered SC or IV at a dose of 75 mg/m²/day for the first week (days 1 through 7 days) or on a 5-2-2 schedule (days 1 through 5 and days 8 and 9) of each 4-week (28-day) cycle

Exposure and compliance will be summarized for each study drug by treatment arm.

7.4.1. Treatment Duration and Exposure

Exposure will be summarized as dose received [cumulative dose, actual dose intensity (DI)] and as dose received relative to planned dose [relative dose intensity (RDI)]. Duration of

exposure to each study drug will be summarized as a continuous variable as well as in categories ($>0 \leq 4$, $>4 \leq 8$, $>8 \leq 12$, $>12 \leq 16$, $>16 \leq 20$, $>20 \leq 24$, and >24 weeks).

Exposure to AG-120 or matched placebo

The dose level for AG-120 or matched placebo is calculated as actual dose administered (mg/day). Only non-zero doses of AG-120 or matched placebo are considered in the derivations.

- Duration of exposure (days) = last dose date – first dose date + 1
- Cumulative dose (mg) = sum of the actual doses
- Planned DI (mg/day) = 500
- Actual DI (mg/day) = cumulative dose (mg) / duration of exposure (days)
- RDI (%) = $100 \times \text{Actual DI (mg/day)} / \text{Planned DI (mg/day)}$

Exposure to Azacitidine

The dose level for azacitidine is calculated as actual dose administered (mg/m²/day). In what follows, dose, last dose date and first dose date refer to azacitidine. Only non-zero doses are considered in the derivations.

- Planned duration of exposure (4-week cycle) = (start date of azacitidine last cycle – start date of azacitidine first cycle + 28) / 28
- Duration of exposure (4-week cycle) = (last dose date – first dose date + 1) / 28
- Cumulative dose (mg/m²) = sum of the actual doses
- Planned DI (mg/m²/4-week cycle) = 525
- Actual DI (mg/m²/4-week cycle) = cumulative dose (mg/m²) / [planned duration of exposure (4-week cycle)]
- RDI (%) = $100 \times \text{Actual DI (mg/m}^2\text{/4-week cycle)} / \text{Planned DI (mg/m}^2\text{/4-week cycle)}$

7.4.2. Dose Modifications

The summary of dose modifications will include:

- The frequency of subjects with at least 1 dose reduction
- Summary of the number of days with dose reductions
- The frequency of subjects with at least 1 interruption of study drug
- Summary of the number of days with interruptions of study drug

Dose reduction is defined as an administered non-zero dose that is lower than the planned dose (AG-120 or matched placebo: 500 mg; azacitidine: 75 mg/m²). Data from the AG-120/Placebo Dosing or Azacitidine Dosing eCRF when the option “Dose Reduced” is chosen will be used in the derivation.

An interruption of study drug is defined as:

- A 0 mg dose given on one or more days for AG-120 or matched placebo, or
- A 0 mg dose given on one or more days within the dosing period (where a subject is not on the “off” part of a treatment cycle) for azacitidine, after which >0 mg dose resumes. Azacitidine will be given 7 days (days 1-7 or days 1-5, 8-9) for each 28-day treatment cycle. The 21 days when azacitidine is not administered following protocol specified dosing regimen will not be considered as a dose interruption. An interruption is not considered a dose change.

Will use the data from the AG-120/Placebo Dosing or Azacitidine Dosing eCRF when the option “Drug Interrupted” is chosen.

7.5. Concomitant Therapies

The following summaries will be presented by treatment arm based on the safety analysis set.

Concomitant medications are defined as non-study medications (from the Prior and Concomitant Medications eCRF) that are started during the on-treatment period or are started before the start of the study treatment and end or remain ongoing during the on-treatment period.

All non-study medications will be coded according to ATC code and PT using the latest version of the WHO Drug Dictionary. All concomitant medications will be summarized in frequency tabulations according to WHO ATC third level and PT.

Concomitant procedures are defined as procedures (from the Prior and Concomitant Procedures eCRF) that are started during the on-treatment period or are started before the start of the study treatment and end or remain ongoing during the on-treatment period.

The concomitant procedures will be coded by the latest version of MedDRA by SOC and PT and will be summarized in frequency tabulations by SOC and PT.

7.6. Subsequent Therapies

The following summaries will be presented by treatment arm based on the FAS. Subsequent therapies are defined as therapies that are started after the last dose of study treatment.

7.6.1. Subsequent Stem Cell Transplants for AML

For subsequent stem cell transplants for AML, type of hematopoietic stem cell transplant (HSCT), and disease status at the time of HSCT will be summarized in frequency tabulations.

HSCT data will be presented in by-subject listings for subjects who receive HSCT.

7.6.2. Subsequent Anticancer Therapies

Subsequent anticancer therapies will be coded according to the ATC code and PT using the latest version of the WHO Drug Dictionary. All subsequent anticancer therapies will be

summarized in frequency tabulations according to the WHO ATC third level and PT. Line of therapy and type of therapy will also be summarized in frequency tabulations.

Anticancer therapies will be presented in by-subject listings for subjects with at least 1 anticancer therapy.

7.7. Efficacy Analyses

The following analyses will be based on the FAS using the IRT randomization stratification factors, unless otherwise specified.

7.7.1. Primary Endpoint

7.7.1.1. Primary Analyses for EFS

EFS is defined as the time from randomization until TF, relapse from remission, or death from any cause, whichever occurs first. TF is defined as failure to achieve CR by Week 24. Subjects who do not achieve CR by Week 24 will be considered to have had an EFS event at Day 1 of randomization. For subjects who achieve CR by Week 24 (responders), the EFS time will be the time from randomization to relapse or death, whichever occurs first.

EFS will be tested using the log-rank test stratified by the randomization stratification factors. The basis for a claim of efficacy will be the statistical significance of EFS in favor of the AG-120+azacitidine arm when the 1-sided p-value <0.025.

Kaplan-Meier estimates (product-limit estimates) will be presented by treatment arm together with a summary of associated statistics. In particular, the EFS rate at 1 day, and 3, 6, 9, 12, 18, 24 and 36 months will be estimated with corresponding 2-sided 95% CIs. The CIs for the survival function estimates at the time points defined above will be derived using the log-log transformation (conftype=loglog default option in SAS PROC LIFETEST) with back transformation to a CI on the untransformed scale. The estimate of the standard error (SE) will be computed using Greenwood's formula.

The HR will be estimated using a Cox's proportional hazards (PH) model stratified by the randomization strata. Each stratum will define a separate baseline hazard function (using the "STRATA" statement in SAS PROC PHREG), ie for the i-th stratum the hazard function is expressed as: $h(i;t)=h(i,0;t)\exp(x\beta)$, where $h(i,0;t)$ defines the baseline hazard function for the i-th stratum and x defines the treatment arm (0= control arm, 1=treatment arm) and β is the unknown regression parameter. Ties will be handled by replacing the proportional hazards model by the discrete logistic model (Ties=Discrete option in SAS PROC PHREG). Given that the PH assumption is not met based on the EFS definition, the overall HR may not be meaningful.

As EFS is a composite endpoint, the estimates for each component will be summarized:

- CR rate by 24 weeks (following the methodology outlined in Section 7.7.2.1 without presenting p-values)
- EFS among subjects who achieve CR by 24 weeks (following the methodology outlined above restricted only to subjects who achieve CR by 24 weeks without

presenting p-values). In addition, the median EFS time with 2-sided 95% CI will be calculated based on Brookmeyer and Crowley.

Restricted Mean Survival Time (RMST)

The HR estimate from the Cox PH model is routinely used to empirically quantify the between-arm difference under the assumption that the ratio of the two hazard functions is constant over time. When this assumption is plausible, such a ratio estimate captures the relative difference between two survival curves. However, the clinical meaning of such a ratio estimate is difficult, if not impossible, to interpret when the underlying PH assumption is violated (ie, the HR is not constant over time).

The RMST is a robust and clinically interpretable summary measure of the survival time distribution. Unlike median survival time, it is estimable even under heavy censoring. There is a considerable body of methodological research (Royston and Parmar, 2011; Uno, et al., 2014; Zhang, 2013) about the use of RMST to estimate treatment effects as an alternative to the HR approach.

The RMST methodology is applicable independently of the PH assumption and can be used, at a minimum, as a sensitivity analysis to explore the robustness of the primary analysis results. However, when large departures from the PH assumption are observed, as is expected in this study for EFS, the log-rank test is underpowered to detect differences between the survival distributions for the treatment arms, and a test of the difference between the RMST for the treatment arm and the control arm may be more appropriate to determine superiority of the treatment arm compared to the control arm with respect to the time-to-event endpoint.

As it pertains to the **cut-off point (τ)** to evaluate the RMST, the cut-off point should not exceed the minimum of the largest observed time for both treatment arms so that the RMST of all treatment arms being evaluated can be adequately estimated and comparison between treatments is feasible; τ should be clinically meaningful and closer to the end of the study follow-up so that the majority of survival outcomes will be covered by the time interval.

$\tau = \min(\text{largest observed survival time for the treatment arm, largest observed survival time for the control arm})$.

The RMST up to time τ can then be interpreted as the expected survival time restricted to the common follow-up time τ among all subjects.

In this section, “survival” is meant to denote EFS.

The treatment effect between the treatment arm and the control arm will also be assessed based on the difference in RMST. The associated 95% CI for the difference in RMST and 1-sided p-value will be generated.

7.7.1.1.1. Determination of Event or Censoring for EFS

Evaluation of disease status, including evaluation of bone marrow and/or peripheral blood, is planned to be conducted at Screening (or as part of Pre-screening if within 28 days prior to randomization); Day 1 (± 7 days) of Weeks 9, 17, 25, 33, 41, 53, and every 24 weeks thereafter; at End of Treatment (EOT); during EFS follow-up on the same schedule; as clinically indicated; and/or any time that disease progression is suspected.

Determination of relapse date

Only disease assessments performed before the start date of subsequent anticancer therapies will be considered in the determination of relapse.

Confirmation is required for relapse. Assessments which are not done or not evaluable are ignored in the derivation of relapse confirmation. A subject will be considered to have relapsed if either of the following criteria are met:

- Relapse in 2 consecutive assessments that are at least 4 weeks apart
- Relapse with no further evaluable disease assessments before discontinuation from study or initiation of subsequent anticancer therapy

The date of relapse considered in the analyses will be the date when the first relapse, that is subsequently confirmed, is observed.

Determination of CR by 24 weeks

CR will be assessed until the date of relapse (that is subsequently confirmed). Only assessments performed on or before the start date of subsequent anticancer therapies will be considered in the determination of CR.

The protocol allows a 1-week window for disease assessments. Therefore, a subject will be considered to have achieved “CR by 24 weeks” if the date of first CR is within 25 weeks (24 weeks target+1 week window) after the date of randomization:

CR by 24 weeks if date of first CR–date of randomization $\leq 24 \times 7 + 7$.

Determination of two or more missing assessments

In the primary analysis of EFS, if a subject has an EFS event (relapse or death) after two or more missing disease assessments, the subject will be censored at the last adequate disease assessment documenting no relapse before the missing assessments. The followings are the rules for determining whether two or more disease assessments are missed.

- If the event date is prior to day 1 of week 53 (relative day since randomization $\leq 52 \times 7 = 364$), and the difference of event date and the last adequate disease assessment $> (8 \times 2 + 1) \times 7 = 119$, then the event is considered as occurring after two or more missing disease assessments
- If the event date is between day 1 of week 53 and day 1 of week 77 (relative day since randomization > 364 and ≤ 532) and the difference of event date and the last adequate disease assessment $> (8 + 12 + 1) \times 7 = 147$, then the event is considered as occurring after two or more missing disease assessments
- If the event date is between day 1 of week 77 and day 1 of week 101 (relative day since randomization > 532 and ≤ 700) and the difference event date and the last adequate disease assessment is $> (12 + 24 + 1) \times 7 = 259$, then the event is considered as occurring after two or more missing disease assessments
- If the event date is after day 1 of week 101 (relative day since randomization > 700) and the difference of event date and the last adequate disease assessment is

$>(24+24+1)\times 7=343$, then the event is considered as occurring after two or more missing disease assessments

The outcome (event or censor), type of event and the date of event or censoring to be considered for the primary analysis of EFS are presented in Table 5.

Table 5: Outcome and Event or Censoring Dates for EFS

Scenario	Date of event/censoring	Event (event type)/ Censored
CR by 24 weeks ^a then relapse	Date of relapse	Event (relapse)
CR by 24 weeks ^a then death (no relapse)	Date of death	Event (death)
CR by 24 weeks ^a then start subsequent anticancer therapy (prior to relapse or no relapse)	Date of the last adequate disease assessment documenting no relapse prior to start of subsequent anticancer therapy or missed response assessments	Censored
CR by 24 weeks ^a then relapse or death after two or more missing or inadequate disease assessments		Censored
CR by 24 weeks ^a and neither relapse nor death		Censored
On treatment ≥ 24 weeks without CR by 24 weeks ^a	Date of randomization	Event (TF, on treatment ≥ 24 weeks without CR)
Treatment discontinuation prior to 24 weeks, without CR by 24 weeks ^a		Event (TF, treatment discontinuation prior to 24 weeks without CR)

Abbreviations: CR = complete response; EFS = event-free survival; TF = treatment failure.

^a Based on the protocol schedule of assessments, "+1 week window" is allowed.

Frequency of subject with each event type and censoring reasons will be presented by treatment arm. Reasons for censoring will be summarized according to the categories in Table 6 following the hierarchy shown.

Table 6: EFS Censoring Reasons and Hierarchy

Hierarchy	Condition	Censoring Reason
1	CR by 24 weeks then start subsequent anticancer therapy	CR by 24 weeks, start subsequent anticancer therapy
2	CR by 24 weeks then relapse or death after two or more missing or inadequate disease assessments	CR by 24 weeks, relapse/death documented after two or more missing disease assessments
4	CR by 24 weeks, no relapse or death, lost to follow-up	CR by 24 weeks, lost to follow-up
5	CR by 24 weeks, no relapse or death, withdrawal by subject from the study	CR by 24 weeks, withdrawal by subject
6	CR by 24 weeks, no relapse or death, ongoing in study	CR by 24 weeks, ongoing without relapse or death

Abbreviations: CR = complete response; EFS = event-free survival.

The EFS event or censoring time, event type and the reason for censoring will also be presented in a by-subject listing.

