12.5.1. Analyses of the Primary Endpoint

The analysis for the primary endpoint will be performed at the time when 173 EFS events have occurred. Event-free survival is defined as the time from randomization until treatment failure, relapse from remission, or death from any cause, whichever occurs first. Treatment failure is defined as failure to achieve CR by Week 24. Subjects who do not achieve CR by Week 24 will be considered to have had an event at Day 1 of randomization. For the remaining CR responders, the event time will be the time of either disease relapse or death, whichever occurs first. Event-free survival will be censored upon initiation of a new anticancer therapy should a new therapy be initiated prior to any EFS event.

Event-free survival will be tested using the log-rank test stratified by the randomization stratification factors (de novo status and geographic region) based on the data in the ITT Analysis Set. The basis for a claim of efficacy will be the statistical significance of EFS in favor of the AG-120 + azacitidine arm when the 1-sided $p \leq 0.025$ (observed EFS HR ≤ 0.742).

The distribution of EFS will be estimated using the KM method. The KM curves and 25th, 50th (median), and 75th percentiles (if estimable), along with their 2-sided 95% CIs, will be presented for each treatment arm. The KM estimates at individual time points (eg, 3-, 6-, and 12-month rates) will also be presented for each treatment arm. A Cox regression model stratified by randomization stratification factors will also be used to estimate the HR of EFS. However, given that the assumption of proportional hazards is not met based on the EFS definition, the overall HR is less meaningful in this context. As EFS is a composite endpoint, the estimates presented separately by each component are more meaningful: CR rate by 24 weeks and EFS among those who have achieved CR by 24 weeks. For subjects who achieve CR by 24 weeks, the KM curves

of the EFS distribution and 25th, 50th (median), and 75th percentiles (if estimable) along with their 2-sided 95% CIs will be presented for each treatment arm. A Cox regression model stratified by randomization stratification factors will also be used to estimate the HR of EFS for these subjects. In addition, the ratio of restricted mean survival time, which does not rely on proportional hazards assumptions, between the 2 arms will also be presented to summarize the treatment effect.

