7.7.2. Key Secondary Endpoints

The key secondary efficacy endpoints are CR, OS, CR+CRh, and OR. CR, CR+CRh and OR will be assessed until the date of relapse (that is subsequently confirmed). Only assessments performed on or before the start date of subsequent anticancer therapies will be considered in the determination of these response endpoints.

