7.7.3. Additional Secondary Efficacy Endpoints

Only disease assessments performed on or before the start date of any further anticancer therapies will be considered in the analyses of these endpoints.

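### The SAP's EFS relapse rule excludes the day new anticancer therapy starts, while its other response cut-offs include it, so a first relapse documented that day is censored in the primary analysis

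*SAP*

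**What the plan says.** SAP 7.7.1.1.1, under the determination of the relapse date, sets the cut-off for EFS: "Only disease assessments performed before the start date of subsequent anticancer therapies will be considered in the determination of relapse". The same section, for CR by 24 weeks, includes the start date: "Only assessments performed on or before the start date of subsequent anticancer therapies will be considered in the determination of CR".

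Two other SAP sections include it as well:
- 7.7.2, for CR, CR+CRh and OR: "Only assessments performed on or before the start date of subsequent anticancer therapies will be considered in the determination of these response endpoints".
- 7.7.3, which covers CR+CRi, the duration endpoints (DOCR, DOCRh, DOR, DOCRi) and the time-to-response endpoints: "Only disease assessments performed on or before the start date of any further anticancer therapies will be considered in the analyses of these endpoints".

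A relapse counts if it is seen at two consecutive assessments at least 4 weeks apart, or under a second criterion: "Relapse with no further evaluable disease assessments before discontinuation from study or initiation of subsequent anticancer therapy". The row of SAP Table 5 that censors responders for new therapy covers CR by 24 weeks "then start subsequent anticancer therapy (prior to relapse or no relapse"), with the censoring date set back to the last relapse-free assessment.

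Protocol 12.5.1 has one sentence on this: "Event-free survival will be censored upon initiation of a new anticancer therapy should a new therapy be initiated prior to any EFS event". Neither document explains why relapse has a different boundary.

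**The concern.** Within one section of the SAP, an assessment dated on the day new therapy starts can establish CR for EFS but cannot establish relapse for EFS. The relapse rule is the only one of the four cut-offs that excludes that day. It is also stricter than the protocol, because therapy that starts on the day a relapse is documented has not clearly started before the event.

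The rule acts on the primary endpoint, and a relapse is a natural reason to start new therapy. An event dropped in this way is therefore not dropped at random with respect to outcome. It also affects EFS among responders, one of the two component summaries that protocol 12.5.1 regards as more informative than the overall hazard ratio. Finally, the boundary has to be coded one way or the other. A choice about primary-endpoint events made after unblinding would be hard to defend.

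**Working it through.** **1. Who is affected.** Subjects without CR by 24 weeks are already events at randomization, so the rule touches only responders. Among them it touches only a *first* relapse dated on the same day as the recorded therapy start. A relapse seen earlier still counts through the second criterion, even if its repeat falls on the start day.

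**2. One subject traced through the rules.** Assessments fall at Weeks 9, 17, 25, 33, 41 and 53, then every 24 weeks, so the next is Week 77. Suppose Week 53 is relapse-free, Week 77 shows a first relapse, and new therapy starts on the Week 77 date.
- Relapse rule: the Week 77 assessment is not before the start date, so it is not used and no relapse is derived.
- Table 5: censored at Week 53, which is 77 - 53 = 24 weeks earlier.
- Same rule with *on or before*: the assessment is used, the second criterion is met, and there is an event at Week 77.
- Between Weeks 41 and 53 the gap is 12 weeks, and between earlier visits it is 8. The ±7-day windows and unscheduled assessments shift these figures.

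**3. The plan's own figures.** Inputs are from SAP 6.2.1 and protocol 12.12: 200 subjects randomized 1:1, CR 20% vs 40%, responder medians 14.6 vs 19.2 months, 173 events, 1-sided 2.5%, 3 then 5 subjects per month, 5% dropout.
- Critical hazard ratio: exp(-2 × 1.960/√173) = 0.742, as in the protocol.
- Power: simulation of the two-component model (failures at day 1, exponential responders; 2,500 replicates, Monte Carlo error √(0.8 × 0.2/2500) = 0.008; stratum proportions assumed) gives 0.803-0.804 for the stratified test with dropout among responders, and 0.792 with dropout among all subjects. The stated 80% is reproduced.

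**4. Events at risk.**
- Treatment failures: 100 × 0.80 + 100 × 0.60 = 140.
- Responder events: 173 - 140 = 33. These include deaths, which the rule does not touch.
- Relapses, assuming 80% of responder events: 33 × 0.80 = 26.4.
- Same-day, assuming 3-10% of relapses: 26.4 × 0.03 = 0.8, and 26.4 × 0.10 = 2.6.

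Neither the 80% nor the 3-10% is in the documents.

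**5. Effect on the test.** The same model was run unstratified (base power 0.82), with a fraction *f* of responder relapses censored and set back by a random 0 to 3.7 months. The 80% relapse share, *f* and the size of the set-back are assumptions.

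| Same-day fraction *f* | Events lost by month 52 | Month of analysis (173 events) | Rejection probability |
|---|---|---|---|
| 0 | 0 | 50.8 | 0.82 |
| 5% both arms | 1.4 | 51.6 | 0.82 |
| 10% both arms | 2.9 | 52.9 | 0.82 |
| 20% both arms | 5.8 | 56.9 | 0.83 |
| 30% both arms | 8.7 | 64.7 | 0.82 |
| 20% control arm only | 2.1 | 52.2 | 0.74 |
| 20% AG-120 arm only | 3.7 | 53.8 | 0.89 |

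The simulated 2.9 at 10% exceeds the 2.6 in step 4 because about 176 events, not 173, are reached by month 52 in the base run. With equal fractions the cost is time, not power. Only an imbalance between arms moves the test, and the imbalances shown use twice the top of the assumed range, in one arm only.

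**The case against.** The strongest reply is that the case is rare and already visible.
- Protocol Table 10 asks for a repeat marrow to confirm relapse, with assessments at least a month apart. Where that is followed, the first relapse assessment precedes new therapy by weeks.
- Protocol 9.13.3 requires study treatment to stop before other anticancer therapy is given.
- SAP 6.5.5 imputes a completely missing therapy start no earlier than the day after relapse, unless the therapy's end date caps it.
- SAP 6.3.6 ignores HSCT conditioning dates.
- SAP 7.7.1.2, sensitivity analysis 1, uses actual relapse dates regardless of new therapy, and censoring reasons are tabulated by arm and listed by subject.

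Most of this stands and is why the effect is put as small. It does not remove the case. Disease is also assessed at EOT and whenever progression is suspected, and blasts reappearing in blood are enough for relapse, so a finding and a therapy start can share a date. The imputation rule suggests that the intent was to keep such relapses. Sensitivity analysis 1 also lifts the missed-assessment censoring, so it does not isolate this rule, and it is not the primary test.

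A reader might infer two stronger contradictions. The first is that Table 5 conflicts with the relapse rule, because it censors for therapy started "prior to relapse or no relapse". The documents do not support that: if Table 5 works on the derived relapse, a same-day case simply has no relapse and fits the row. The second is that EFS and DOCR must disagree about the same subject. That is conditional. DOCR is defined through confirmed relapse, and the only derivation of confirmed relapse is in 7.7.1.1.1, so DOCR may inherit the stricter boundary. The two differ only if the 7.7.3 sentence governs, and the SAP does not say which applies.

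**Conclusion.** The inconsistency is real. The EFS relapse boundary is stricter than the SAP's other three cut-offs and than the protocol's censoring sentence, no reason is given, and a first relapse documented on the therapy start date is censored and set back in the primary analysis.

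Its size is probably 1 to 3 events (0.8 to 2.6) out of 173, resting on the assumed 80% relapse share and 3-10% same-day share. The sample size and the stated 80% power are unaffected.

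A reader might go further and infer material bias or lost power in the primary test. The documents do not support that. With equal same-day rates the simulated power stays at 0.82-0.83, and nothing in a double-blind design points to unequal rates. This is a minor but worthwhile correction to a primary-endpoint rule.

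**What to change.** In SAP 7.7.1.1.1:
- For relapse, change the cut-off from *before* to *on or before* the start date of subsequent anticancer therapy.
- Apply the same boundary to the second relapse criterion. State the result when a start-day assessment follows an earlier unconfirmed relapse, since it would then count as a further evaluable assessment.
- Add to Table 5 that a relapse documented on the day new therapy starts is an event at that date.

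The cost is a small wording change and the matching derivation code, with no new data and no burden on subjects. It should be made before unblinding. If the stricter boundary is intended, the SAP should give the reason and say whether it also governs the duration endpoints.
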